### Study Day

Post study day 1: study day= (date - date of Study Day 1) + 1

Pre study day 1: study day= (date – date of Study Day 1)

### Study Day 1

Study day 1 is defined as the first day of administration of AMG 820 after enrollment.

The day prior to Study Day 1 is considered Day -1.

### Time to Response per irRECIST (TTR)

Time to response is defined as the time from first dose of AMG 820 until first documented complete or partial response per irRECIST. The following censoring strategies will be used:

If a subject has not responded during the study, TTR will be censored at the last evaluable radiological assessment date.

If a subject has no tumor evaluation in the study, TTR will be censored at the date of the first administration of AMG 820.

### Time to progression per irRECIST (TTP)

Time to progression is calculated as the number of days from the first administration of AMG 820 to the first objective assessment of disease progression as per irRECIST, clinical progression, or if applicable date of censoring (date of progressive disease or censoring – date of first administration of AMG 820 +1). The following censoring strategies will be used:

If a subject's disease has not progressed, time to progression will be censored at the last date they are known to be progression-free (ie, the last evaluable radiological assessment date).

If a subject has no tumor evaluation in the study, time to progression will be censored at the date of the first administration of AMG 820.

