^j Radiographic imaging (CT or MRI) of the chest, abdomen and pelvis, and MRI of the brain if a subject has signs and symptoms suggestive of CNS metastases, are required at screening. MRI of the brain is required for all NSCLC subjects at screening. Tumor assessments must also include all other sites of disease. The screening scans must be done within 28 days prior to enrollment. During treatment, radiographic imaging (CT or MRI) of the chest, abdomen and pelvis, along with tumor assessments of all other sites of disease, (MRI of the brain if a subject has symptoms or signs suggestive of CNS metastases), will be performed independent of treatment cycle at week 10 (± 1 week), and then every 10 weeks (± 2 weeks) or more frequently if clinically indicated until confirmed PD per irRECIST or start of new anticancer treatment. Imaging should not be adjusted for cycle initiation delays and performed according to the calendar. The imaging modality selected (eg, CT or MRI) should remain constant for any individual subject. Response or progression should be confirmed by repeated radiographic imaging ≥ 4 weeks after the first indication of response or progression. Radiographic imaging is required at the safety follow-up visit if the subject ended treatment prior to confirmed PD and has not had radiographic tumor imaging performed within 6 weeks (+1 week) of the visit. The radiographic images will be submitted to a central imaging lab.

^k PK samples should be collected at the exact nominal time point as noted, where collection times are to be defined relative to the end of AMG 820 infusion. If unable to collect a PK sample at the specified nominal time point collect it as close as possible to the nominal time point and record the actual collection time. PK samples not collected at exact nominal time point will not be considered protocol deviations.

^m Safety labs should be performed and reviewed within 2 days prior to each dose.

ⁿ CEA for CRC and CA 19-9 for pancreatic cancer every 6 weeks ± 2 weeks

^o For subjects who discontinued treatment for any reason other than confirmed PD, every effort should be made to perform radiographic imaging (CT or MRI) of the chest, abdomen and pelvis, along with tumor assessments of all other sites of disease every 12 weeks until documentation of confirmed PD per irRECIST, clinical progression, start of new anticancer therapy, or up to 12 months after subject's enrollment for the study, whichever occurs first.

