7.2.3 Safety Follow-up Visit(s)

All subjects will complete a safety follow-up visit approximately 135 (+7) days after the last dose of study treatment.

The following procedures will be performed:

- Physical examination as per standard of care including ECOG performance status assessment. Physical examination findings should be recorded on the appropriate CRF (eg, medical history, event)
- Body weight in kilograms should be measured without shoes.
- Vital signs (systolic/diastolic blood pressure, heart rate, respiratory rate, temperature): Subject should be in a supine position in a rested and calm state for at least 5 minutes before blood pressure assessments are conducted. If the subject is unable to be in the supine position, the subject should be in most recumbent position as possible. The position selected and temperature location for a subject should be the same that is used throughout the study and documented on the vital sign CRF. Record all measurements on the vital signs CRF
- A 12-lead ECG per standard of care: The ECG must include the following measurements: heart rate, PR, QRS, QT and QTc intervals. Subject must be in supine position in a rested and calm state for at least 5 minutes before ECG assessment is conducted. If the subject is unable to be in the supine position, the subject should be in most recumbent position as possible. The investigator or designated site physician will review all ECGs. Once signed, the original ECG tracing will be retained with the subject's source documents. At the request of the sponsor, a copy of the original ECG will be made available to the Sponsor.
- Local laboratory Assessments
 - hematology panel
 - chemistry panel
 - lipase and amylase
 - coagulation: PT or INR and PTT or a PTT
 - thyroid function tests: T3 (or FT3), FT4, TSH
 - urinalysis
 - serum or urine pregnancy test for female subjects of childbearing potential

- Central laboratory assessments (refer to Schedule of Assessments as not all tests will be required after Amendment 2):
 - All subjects
 - Blood for immunogenicity
- Radiographic tumor imaging and tumor response assessments are to be performed if the subject ended study treatment prior to confirmed PD per irRECIST and has not had assessments performed within 6 weeks of the visit.

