 - Subjects with a global deterioration of health status requiring discontinuation of treatment without radiographic confirmation of disease progression (confirmed irPD) at the time should have the reason for treatment discontinuation classified as 'clinical disease progression'. In this case, irPD cannot be assigned at the time as the overall objective tumor response. Every effort should be made to radiographically confirm irPD even after discontinuation of treatment.

Measurement and Tumor Response Assessment Based on modified irRECIST	
Measurable lesions	
 • ≥ 10 mm (unidirectional measure) • Pathologic lymph nodes: short axis ≥ 15 mm
Measurement of each lesion	The longest diameter (mm)
The sum of the measurements (SLD)	
 • The sum of the longest diameters (SLD) of all index lesions and new measurable lesions, if any • Up to 5 lesions per organ, up to 10 total
Response assessment	
 • irPD: $\geq 20\%$ increase from nadir and at least 5 mm absolute increase compared to nadir (requires confirmation) • irSD: $< 30\%$ decrease from baseline and $< 20\%$ increase from nadir • irPR: $\geq 30\%$ decrease from baseline (requires confirmation) • irCR: Disappearance of all lesions (requires confirmation)
New Lesions	The presence of new lesion(s) does not define progression. Measurable new lesions (≥ 10 mm): The measurements of the new lesions(s) are included in the SLD
Confirmation	Confirmation by 2 consecutive observations at least 4 weeks apart required for irCR, irPR and irPD.

Modified irRECIST Overall Response Assessment			
Measurable Response	Non-measurable Response		Overall Response
Index and new measurable lesions (tumor burden) ^a , %	Non-Index lesions	New non-measurable lesions	Using irRECIST
↓ 100%	Absent	Absent	irCR ^b
↓ 100%	Stable/NA	Any	irPR ^b
↓ 100%	Unequivocal progression	Any	irPR ^b
↓ $\geq 30\%$	Absent/Stable/NA	Any	irPR ^b
↓ $\geq 30\%$	Unequivocal progression	Any	irPR ^b
↓ $< 30\%$ to ↑ $< 20\%$	Absent/Stable/NA	Any	irSD
↓ $< 30\%$ to ↑ $< 20\%$	Unequivocal progression	Any	irSD
↑ $\geq 20\%$	Any	Any	irPD ^b
UE	Any	Any	UE
ND	Any	Any	UE
NA	Any	Any	UE

NA = not available; ND = not done; UE = unable to evaluate

^a Decrease assessed relative to baseline, including new measurable lesions (≥ 10 mm)

^b Response (irCR, irPR) and progression (irPD) are confirmed by a second, consecutive assessment at least 4 weeks apart.

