#### Duration of Response

Duration of response is defined as the number of days between the date of the first tumor assessment indicating an objective response through to the subsequent date of progression as classified by irRECIST or death, or where applicable date of censoring [date of first progressive disease assessment or death or date of censoring – date of the first objective response result +1]. Subjects who respond and have not progressed while on study or died will be censored at the date of the last evaluable radiological assessment. Subjects who do not achieve an objective response will be excluded from the analysis of duration of response.

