#### Investigational Product

The term 'investigational product' is used in to reference to AMG 820 in combination with pembrolizumab.

---

Last Investigational Product Dose Date

The last AMG 820 dose date for each subject is defined as the latest date AMG 820 is administered.

Objective Response as per irRECIST (irOR)

Objective response is defined as a complete response or partial response, as defined by the irRECIST. Confirmation is done by a repeat, consecutive assessment no less than 4 weeks from the date of first documented assessment.

Objective Response Rate as per irRECIST (irORR)

Immune-related ORR (irORR) is defined as the percentage of subjects with irOR.

Overall Survival Time

Overall survival time is calculated as the number of days from the first administration of AMG 820 to death or if applicable censoring [(date of death or censoring – date of first dose of AMG 820 + 1)]. Subjects who withdraw from treatment without withdrawing consent will be followed for survival status up to 12 months.

Subjects who are alive (no record of death) and are lost to follow-up will be censored at the date of last contact.

Progression-Free Survival Time per irRECIST (PFS)

Progression-free survival time is calculated as the number of days from the first administration of AMG 820 to the first assessment of disease progression as per irRECIST or death due to any cause, or if applicable date of censoring (date of progressive disease or death or censoring – first administration of AMG 820 +1).

The following censoring strategies will be used for the progression free survival analysis:

If a subject's disease has not progressed and the subject is alive, progression-free survival time will be censored at the last date they are known to be progression-free (ie, the last evaluable radiological assessment date).

If a subject has no tumor evaluation in the study, progression-free survival time will be censored at the date of the first administration of AMG 820.

Subjects who withdraw consent to participate in the study prior to disease progression will be censored at their last evaluable radiological assessment date.

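### Three secondary time-to-event rules in SAP Sections 6 and 10.6.2 (the TTP event, day-1 censoring, all-subject Kaplan-Meier of TTR) give incoherent or biased estimates if followed as written

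*SAP*

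**What the plan says.** **TTP, PFS and DOR.** SAP Section 6 gives TTP an irRECIST heading and measures it from first dose to "the first objective assessment of disease progression as per irRECIST, clinical progression, or if applicable date of censoring". The bracketed formula that follows names only the date of progressive disease or of censoring. PFS runs from first dose "to the first assessment of disease progression as per irRECIST or death due to any cause". DOR runs from first response "through to the subsequent date of progression as classified by irRECIST or death". Neither mentions clinical progression. Protocol Appendix D keeps the two ideas apart: if treatment stops for deteriorating health without confirmed irPD, the reason is recorded as clinical progression, and "In this case, irPD cannot be assigned at the time as the overall objective tumor response".

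**Patients without a tumor evaluation.** For PFS, "progression-free survival time will be censored at the date of the first administration of AMG 820". For TTP, "time to progression will be censored at the date of the first administration of AMG 820". The PFS censoring rule just before this one is restricted to patients who are alive; this one carries no such restriction.

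**TTR.** SAP Section 6 censors every non-responder at the last evaluable scan, or at first dose if there is none. It makes no distinction for patients who have progressed or died. SAP 10.6.2 plans Kaplan-Meier curves for OS, PFS, TTR, DOR and TTP with rates at selected weeks, and adds a TTR analysis restricted to responders.

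**The concern.** These endpoints appear side by side in the same listings and curves, so a reader will expect one meaning of progression across them. As written, a patient can have progressed in TTP while remaining progression-free in PFS, and still responding in DOR, at the same date.

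The other two rules affect the estimates themselves. If the day-1 rule is programmed literally, the earliest deaths drop out of PFS. If patients who can no longer respond are censored in TTR, the curve estimates response in a hypothetical group in which nobody progresses or dies first. It can then end above the response rate reported as the primary result. Two competent programmers could also read the first two rules differently and obtain different PFS and TTP results from the same data.

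**Working it through.** The plan states no figure for this point, so there is nothing to reproduce. The check compares the definitions and then applies product-limit arithmetic to assumed data.

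**1. One patient under the three definitions (assumed history).** irSD at week 10, last dose on day 85, clinical progression at week 14, no irPD documented, death at week 30.
- End-of-treatment scan (Protocol 7.4): needed if the last scan is 6 or more weeks old. Here 14 − 10 = 4 weeks, so it is not triggered.
- Safety-visit scan (Protocol Table 5, footnote j): "Radiographic imaging is required at the safety follow-up visit if the subject ended treatment prior to confirmed PD". The visit is 135 (+7) days after last dose: 85 + 135 = day 220 to 85 + 142 = day 227. That is (220 − 1)/7 = 31.3 to (227 − 1)/7 = 32.3 weeks after first dose. The patient has died by then.
- Result: TTP is an event at week 14. PFS is an event at week 30, so the patient counts as progression-free at 6 months (week 26).

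An extra scan to document irPD, which Appendix D encourages, would narrow the gap. However, Protocol 7.2.4 lets follow-up imaging stop at clinical progression.

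A responder shows the same split in DOR. With response on day 70, clinical progression on day 200 and death on day 260, TTP is an event on day 200. DOR is 260 − 70 + 1 = 191 days, against 200 − 70 + 1 = 131 days if clinical progression counted.

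**2. Day-1 censoring and 6-month PFS (assumed data, n=29).** k patients die on day 50, before the week-10 scan. Of the others, half (rounded down) have irPD on day 70 and the rest progress on day 210. PFS is read at day 182.

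| k (share) | Death counted as event | Censored at day 1 | Difference |
|---|---|---|---|
| 3 (10%) | 13/29 = 44.8% | 13/26 = 50.0% | 5.2 points |
| 6 (21%) | 12/29 = 41.4% | 12/23 = 52.2% | 10.8 points |
| 9 (31%) | 10/29 = 34.5% | 10/20 = 50.0% | 15.5 points |

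**3. All-subject Kaplan-Meier of TTR.** Each response adds S/Y to 1 − KM, where S is the estimate just before it and Y is the number at risk. S/Y starts at 1/n. Responses leave it unchanged and each censoring raises it. The final 1 − KM is therefore at or above responders/n.

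Assumed data, with responses at weeks 10 and 20 and non-responders who progressed or died censored at week 10:
- n=43, 5 then 3 responses, 24 censored: 1 − (38/43)(11/14) = 30.6%. With 12 censored: 1 − (38/43)(23/26) = 21.8%. ORR = 8/43 = 18.6%.
- n=29, 2 then 2 responses, 18 censored: 1 − (27/29)(7/9) = 27.6%. With 9 censored: 1 − (27/29)(16/18) = 17.2%. ORR = 4/29 = 13.8%.

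At week 10 in the n=43 case both methods give 5/43 = 11.6%. The excess appears only with responses after others have been censored. If everyone is scanned and all responses fall at the first scan, the curve equals the ORR.

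**The case against.** **TTP.** The bracketed formula omits clinical progression, so TTP can be read as already excluding it. The protocol also recognises clinical progression elsewhere: it can end follow-up imaging, and need for palliative radiation is a sign of it. Counting it in all three endpoints would therefore be a reasonable alternative. Removing it from TTP has a price, because patients the investigator considers progressed are censored at their last scan, possibly informatively. All of this stands. It shows that the direction of the change is a choice, but the mismatch remains under either choice.

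A reader might infer that PFS longer than TTP is itself the error. The documents do not support that. TTP excludes death, so a patient who dies without irPD normally has a censored TTP shorter than PFS. With clinical progression removed, the worked patient would have TTP censored at week 10 and PFS of 30 weeks. The incoherence is narrower: a TTP progression event at a date when PFS still counts the patient as progression-free.

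**Day-1 censoring.** Both definitions introduce censoring only where applicable, and PFS counts death from any cause. The natural reading is that an event prevails. That is fair, but the preceding PFS rule is expressly limited to living patients and this one is not, so the literal reading is available.

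**TTR.** The responder-only analysis is already planned, the protocol synopsis treats Kaplan-Meier presentation as optional, and nothing calls 1 − KM a response rate. This softens the point. The SAP nonetheless commits to the all-subject curve, with the responder-only analysis in addition to it.

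**Consequence.** These are descriptive secondary endpoints without formal tests, and the protocol amendment records that the sponsor had decided to stop investigating the combination. That limits the severity. The SAP still governs the final analysis.

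**Conclusion.** The point holds on all three counts and is minor. The TTP mismatch follows from the text alone; the documents do not say how many patients have clinical progression without irPD. The day-1 effect of about 5 to 15 points on 6-month PFS rests on the literal reading, on an assumed 10 to 30% dying before the first scan, and on the assumed progression pattern. That TTR's final 1 − KM is at or above the ORR follows from the method, given the same responders in both; the size of the excess depends on the assumed timing.

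Two further inferences go too far. First, a reader might conclude that main PFS is wrong because it omits clinical progression, and measure the error by how far 6-month PFS would fall if it were counted. Under the irRECIST label PFS is correctly defined and would not change under the TTP repair recommended here. Such a calculation would also have to treat a single safety-visit scan as irPD, although Appendix D requires a second scan at least 4 weeks later. Secondly, the primary ORR and the Simon stage decisions use none of these rules and are unaffected.

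**What to change.** 1. Use one progression rule for TTP, PFS and DOR. To match the irRECIST heading, remove clinical progression from main TTP. Because this censors clinical progressors at their last scan, report TTP and PFS with clinical progression as an event in a labelled sensitivity analysis, and state how it is dated.
2. State that censoring at first dose applies only to patients with no recorded event: death for PFS, and clinical progression wherever it counts as an event. Say whether a tumor evaluation on study means a post-baseline scan.
3. Replace the all-subject Kaplan-Meier of TTR with a cumulative incidence of response, with death and progression that ends response follow-up as competing events. Alternatively, keep only the responder-only TTR already in SAP 10.6.2.

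The cost is a few SAP sentences and minor programming. The main analyses need no new data. The sensitivity analysis needs a clinical-progression date; long-term follow-up collects disease status, but the sponsor should confirm that the CRF holds the date.

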### Treatment-Emergent Adverse Event( TEAE)

A treatment-emergent adverse event is any adverse event starting on or after the first dose of AMG 820 **or pembrolizumab**, as determined by the flag indicating if the adverse event started prior to the first dose on the Adverse Events Summary CRF, and up to and including **135 [+7]** days after **the last dose of AMG 820 or pembrolizumab, whichever is later.**

---

### Treatment-Related Adverse Event

Treatment-related AEs are adverse events deemed by the investigator to be possibly or probably related to AMG 820 or pembrolizumab. The investigator must assess whether the adverse event is possibly related to any study-mandated activity (eg, administration of investigational product, protocol-required procedure (including any screening procedure(s))). This relationship is indicated by a “yes” or “no” response to the question: “Is there a reasonable possibility that the event may have been caused by a study activity.” If the severity of an adverse event changes from the date of onset to the date of resolution, record a single event for each level of severity on the Event CRF.

The Investigator is expected to follow reported adverse events until stabilization or reversibility.

## **7. Analysis Subsets**

The analysis of all endpoints, unless noted otherwise, will be conducted on the Safety Analysis Set.

### **7.1 Safety Analysis Set**

The Safety Analysis Set will consist of all subjects that are enrolled and receive at least 1 dose of AMG 820.

### **7.2 Dose Limiting Toxicity Analysis Set**

The Dose Limiting Toxicity Analysis Set will contain DLT-evaluable subjects (see protocol section 6.2.1.2.2 for definition of DLT-evaluable).

### **7.3 Pharmacokinetic (PK) Analysis Set**

The PK concentration analysis set will contain all subjects who have received at least 1 dose of AMG 820 and have at least one PK sample collected.

## **8. Interim Analysis and Early Stopping Guidelines**

### **8.1 Interim Analysis**

Safety and all clinical data will be monitored on an ongoing basis. All available cumulative data will be reviewed in Part 1 by cohort, prior to making dose escalation decisions, by the Dose Level Review Team (DLRT). In study Part 2 stage 1, similar assessments will be held after each set of 20 subjects have enrolled through the end of Part 2 stage 1 enrollment.

In Part 2, a Simon Two-Stage design is used for all groups (Group 1, 2, 3, 4a, 4b) with the first stage enrolling n=18, 10, 19, 10 and 10 subjects, respectively (see [Figure 1](#) of Study Schema). Each group will enroll subjects to a first stage. The second stage for

each group will be enrolled depending on clinical activity from stage 1, evaluated when the subjects have been treated for at least 6 months or earlier if the required number of responders have been reached. The pre-planned recommendations for enrollment to stage 2 are based on ORR per local irRECIST, however the DLRT will make the decisions for stage 2 enrollment after reviewing all available safety, efficacy, pharmacokinetic and pharmacodynamic data.

The study may be discontinued or modified at any time due to documented safety findings.

